12.3.2 Anesthesia Management Adverse Events

During anesthesia, the events listed below will be captured:

- Hypotension and hypertension >20% from baseline, cardiac arrest or clinically significant changes in Heart Rate or Blood Pressure >20% from baseline
- The respiratory complications involving:
 - laryngospasm
 - bronchospasm
 - desaturation (SpO₂<90%, of any duration)
 - hypercarbia (PCO₂=55mmHg)
- Events related to movement, grimacing, eye opening, tearing, sweating, mydriasis

12.3.3 BIS™ Sensor

Potential risks associated with the BIS™ sensor, as well as risk minimization, are discussed within *Section 11.* The use of the BIS™ sensors may cause minor discomfort, an allergic reaction or skin irritation such as redness, itching, swollenness and redness, water-filled blister, and reddened scar tissue. These events will be collected during the study.

12.3.4 Adverse Events Reported in Literature

Potential adverse events and patient complications associated with BIS™ sensor reported in the literature, including skin integrity/pressure sores, rash, ecchymosis/heat wounds.

Skin integrity and reactions will be assessed just after sensor removal. All mild events that resolve within 48 hours after sensor removal are anticipated and will not be considered as reportable AE. If pronounced erythema and papules, or vesicular eruption are visible, on the subject's skin after sensor removal or if the subject requires any medical intervention related to the skin event then this event will be considered as AE. For more events and risk assessments, refer to *Section 10.*

In addition, the skin assessment will be reviewed by the Clinical Study Manager (CSM) and Medical Advisor in accordance with Clinical Safety Management and Potential complaint Plan. If the sponsor assessment of event classification differs from those opinions of the reporting investigator, the CSM communicates both opinions to the Site and Medtronic Complaint Handling Unit as needed.

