Safety Assessments	
This is a prospective, randomized, controlled study where the only change in routine management is the placement of the BIS™ monitor probe on the forehead. The choice of sedative drugs, dose, and route of administration will be based on clinical indications as judged by the attending Anesthesiologist, and it will not be changed for the study.
 
The BIS™ monitor will not be used in situations where the placement of the probe will interfere with a procedure, cause scan artifacts, or where the presence of a metal monitor is contraindicated (e.g., MRI scans). Therefore, we believe there is only a minimal increase in risks from participating in the study. This risk relates to the possibility of developing irritation to the skin at the site of placement.

	
Subjects will be monitored for Adverse Events, Serious Adverse Events, and Device-Related Adverse Events from BIS™ sensor applications throughout the BIS™ sensor removal.

Statistics	
Standard demographic information and baseline characteristics will be summarized using descriptive statistics. For safety assessments, adverse events (AEs) will be summarized using frequency counts and percentages. Descriptive statistics will be provided by severity and relationship as needed.
 
The primary analysis will be based on all evaluable data (excluding training subjects). Normality of data will be tested using the Kolmogorov-Smirnov test. Depending on whether normality assumption hold, a two group t-test or Wilcoxon rank-sum test will be used to compare between the two treatment groups. A P-value of less than 0.05 is considered statistically significant unless otherwise specified.
 
The secondary endpoints will be evaluated using the Holm-Bonferroni method to ensure the overall type I error rate is controlled at the 0.05 level.
 
Cardiovascular Variables will be summarized for both groups. The incidence of hypotension will be summarized and compared to anesthesia sedation levels.
 
The anesthetic requirements with the BIS™ value, the percentage of time during maintenance with BIS™ values within the specified ranges, and number of episodes and duration of burst suppression will be assessed for both treatment groups.
 
Additional endpoints, including PAED scale, Pain Rating Score and a subgroup analysis for subjects requiring neuromuscular blockade, will be summarized using descriptive statistics for each group and groups combined.

4. Introduction

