6.1. Duration

The planned duration of the study is 8 - 12 months. The consented study subject duration of participation is not to exceed the duration of the surgery and post-surgical discharge.

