12.1 Adverse Events

AE definitions are provided in Table 6.

AE information will be collected throughout the study from the enrollment through study exit.

A list of anticipated adverse events and risks that are expected in nature is included in Section 10.

Reporting of these events to Medtronic will occur via prompt email and the AE eCRF. Each event must be reported separately. Documented pre-existing conditions are not considered AEs unless the nature or severity of the condition has worsened.

For AEs that require immediate reporting (see Table 7), initial reporting must be done by email, phone, , and then on the eCRF completing as much information as possible. The completed AE eCRF must be submitted to Medtronic as soon as possible.

Any medication/treatment associated with the treatment of an AE must be reported

All AEs considered at least possibly related to the study will be followed until resolved, stabilized, and/or returned to baseline.

Medtronic will immediately conduct an evaluation of reported events. Table 5 shows event reporting requirements. At a minimum, the following information will be recorded:

- A description of the event
- The date of event onset
- The relatedness of the event to the device
- Actions are taken as a result of the event
- The outcome of the event

Table 5: Definition of Adverse Events and Device Deficiencies

General	
Adverse Event (AE)	
Any untoward medical occurrence, unintended disease or injury, or untoward clinical signs (including abnormal laboratory findings) in subjects, users or other persons, whether or not related to the investigational medical device.
 
NOTE 1: This definition includes events related to the investigational medical device or the comparator.
 
NOTE 2: This definition includes events related to the procedures involved.

Medtronic Business Restricted

	
NOTE 3: For users or other persons, this definition is restricted to events related to investigational medical devices.

Adverse Device Effect (ADE)	
Adverse event related to the use of an investigational medical device.
 
NOTE 1: This definition includes adverse events resulting from insufficient or inadequate instructions for use, deployment, implantation, installation, or operation, or any malfunction of the investigational medical device.
 
NOTE 2: This definition includes any event resulting from use error or from intentional misuse of the investigational medical device.

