12.2.2 Adverse Event and Device Deficiency Reporting Requirements

Regulatory reporting of AEs and DDs will be recorded and reported according to local regulatory requirements. It is the responsibility of the Investigator and the sponsor to abide by the AE reporting requirements stipulated by local law and the study site's IRB.

Table 7: Reporting Requirements for Events

Serious Adverse Device Effects (SADE), including Unanticipated Adverse Device Effect (UADE):	
Investigator submits to:	
Medtronic	Within 24 hours after the investigator first learns of the event.
Regulatory Authority	As per local reporting requirements.
IRB	Submit to IRB per local reporting requirement.
Sponsor submits to:	
Regulatory Authorities	Reporting timeframe as per local requirement.
IRB	Submit to IRB per local reporting requirement.
Serious Adverse Events (SAE)	
Investigator submits to:	
Medtronic	Within 24 hours after the investigator first learns of the event.
Regulatory Authority	As per local reporting requirements.
IRB	Submit to IRB per local reporting requirement.
Sponsor submits to:	
Regulatory Authorities	Reporting timeframe as per local requirement.
IRB	Submit to IRB per local reporting requirement.
Adverse Device Effects (ADE)	
Investigator submits to:	
Medtronic	Within 24 hours after the investigator first learns of the event.
Sponsor submits to:	
Regulatory Authority	As per local reporting requirements.
IRB	Submit to IRB per local reporting requirement.
Sponsor submits to:	
Regulatory Authorities	Reporting timeframe as per local requirement
IRB	Submit to IRB per local reporting requirement.
All other AEs	
Investigator submits to:	
Medtronic	Submit as soon as possible, but no later than within 10 working days after the investigator first learns of the event.
Regulatory Authority	As per local reporting.
IRB	Submit to IRB per local reporting requirement.
Device Deficiency with SADE potential	
Investigator submits to:	
Medtronic	No later than 48 hours after the investigator first learns of the event.
Regulatory Authorities	As per local reporting requirements.
IRB	As per local reporting requirement.
Sponsor submits to:	
Regulatory Authorities	As per local reporting requirements.
IRB	As per local reporting requirement.
All other Device Deficiencies	
Investigator submits to	

Medtronic Business Restricted

Medtronic	No later than 48 hours after the investigator first learns of the event.
Regulatory Authorities	As per local reporting requirements.

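### Mild sensor-site skin reactions can drop out of every planned safety table, under a 48-hour rule that no scheduled observation supports

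*Protocol*

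**What the plan says.** - **Protocol 12.3.4** schedules one look at the skin: "Skin integrity and reactions will be assessed just after sensor removal". It then exempts a class of findings: "All mild events that resolve within 48 hours after sensor removal are anticipated and will not be considered as reportable AE". The next sentence, beginning "If pronounced erythema and papules, or vesicular eruption are visible", keeps more marked reactions, and any needing medical intervention, as AEs. The assessment is also reviewed by the study manager and the Medical Advisor.
- **Protocol 12.3.3** lists discomfort, redness, itching, blistering and similar sensor effects and says: "These events will be collected during the study".
- **Protocol 6.1** says that participation "is not to exceed the duration of the surgery and post-surgical discharge". Section 10.14.1 adds that nothing further is collected after exit.
- **Protocol 12.1** defines an adverse device effect as: "Adverse event related to the use of an investigational medical device". Table 7 in 12.2.2 asks the investigator to report such effects to the sponsor: "Within 24 hours after the investigator first learns of the event".
- **Protocol Synopsis, Safety Assessments**, on the small increase in risk from taking part: "This risk relates to the possibility of developing irritation to the skin at the site of placement". Section 10.9.7 says much the same. Section 11.1.1 calls minor irritation probable and usually over within hours.
- **SAP 7.10** summarises adverse events by counts and percentages, by severity and relationship. It mentions no other skin data.

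**The concern.** Whether a mild reaction counts depends on something the study does not arrange to observe. At sensor removal the assessor can grade a reaction but cannot know whether it will be gone in 48 hours. If it is assumed that it will be, the reaction is not a reportable AE, and no other planned table would show it.

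The protocol's minimal-risk argument rests on skin irritation being the added risk. All children in both arms wear the sensor, so there is no unexposed group, and the recorded count is the trial's only evidence on that risk. A low or zero count of mild reactions in the study report could be read as a finding about the sensor when it partly reflects the definition.

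**Working it through.** No figure in the plan is at issue, so there is none to reproduce. The check is mainly a comparison of texts.

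**Step 1: can the 48-hour condition be observed?**

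| Source | Observation or AE window |
|---|---|
| Protocol 12.3.4 | one skin check, just after sensor removal |
| Protocol 6.1 and 10.14.1 | participation to discharge; nothing collected after exit |
| Protocol 10.9.7 and SAP 7.10 | sensor application to sensor removal |
| Protocol 12.1 | enrollment to study exit |
| Protocol 10.11 | procedure plus 48 hours |

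Only 10.11 reaches 48 hours, and no visit or call is scheduled to support it. Under 10.9.7 and SAP 7.10, the required skin check itself falls just after monitoring has ended. A child still in hospital could be looked at, and a reaction that clears before discharge could be noticed, but nothing schedules either look. A mild reaction lasting beyond 48 hours is nominally reportable, with nobody assigned to see it.

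**Step 2: does follow-up of AEs fill the gap?** Section 12.1 follows AEs that are at least possibly related to the study until they resolve or stabilise, and 10.14.1 recommends similar follow-up before exit. Both apply to AEs. Under 12.3.4, a mild reaction's status as a reportable AE depends on its duration, so the follow-up that would establish the duration is triggered only if the status is already settled. That is circular.

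**Step 3: where would a mild finding appear?** The schedule of events (Table 5 in Protocol 10.2) has rows for sensor placement, adverse events and device deficiencies, but none for skin assessment. SAP 7.10 tabulates AEs only. A mild finding could be recorded at the check and still have no table to go into.

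**Step 4: size, for illustration.** The documents give no skin-reaction rate, so the rate p is assumed. The base is the minimum of 108 qualifying data sets (Protocol 14.2). Adding the 16 to 32 training children gives 108 + 16 = 124 to 108 + 32 = 140. The expected count is n × p, and P(at least one) = 1 − (1 − p)^n.

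| Assumed p | Expected, n = 108 | P(at least one), n = 108 | Expected, n = 124 to 140 |
|---|---|---|---|
| 1% | 1.08 | 66.2% | 1.24 to 1.40 |
| 5% | 5.4 | 99.6% | 6.2 to 7.0 |
| 10% | 10.8 | above 99.9% | 12.4 to 14.0 |
| 20% | 21.6 | above 99.9% | 24.8 to 28.0 |

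If all of these were treated as exempt, the AE table would show none. A reader who took 0/108 at face value would compute a one-sided 95% upper bound of 1 − 0.05^(1/108) = 2.7%. The plan computes no such bound, and it would not be valid for mild reactions if they were left out by definition.

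**The case against.** The strongest reply is that 12.3.4 is a deliberate rule for a trivial event class. Pronounced, vesicular or treated reactions remain AEs, and the visible signs are judged on the skin after removal without any 48-hour wait. The exempt reactions are mild, 11.1.1 already discloses them, both arms wear the sensor, and no primary or secondary endpoint is involved. All of that stands, and it limits the point to mild reactions and to safety reporting.

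Four stronger readings are tempting, and the documents do not support them:

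- *Sensor skin harm as a whole could be reported as zero.* The sentence after the exemption rules this out. Nor is irritation the only sensor risk: 11.1.1 also lists pressure injury, shock and burn.
- *Sections 12.3.3 and 12.3.4 contradict each other.* A finding can be collected at the skin check without being a reportable AE. What is missing is any statement of how it is then tabulated.
- *The 24-hour clock in Table 7 makes the rule impossible.* That follows only if the general device-effect definition in 12.1 overrides 12.3.4. If 12.3.4 governs, the clock never starts. The documents do not say which prevails.
- *Children leave within about half an hour.* The discharge times of roughly 20 to 27 minutes in Protocol 4.1.3.2 are readiness times from an earlier study's tonsillectomy and adenoidectomy group. They do not establish time to discharge in this trial.

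It can also be said that 10.11 supplies a 48-hour window matching the exemption. It does so in words, but it has no contact behind it and conflicts with 6.1, 10.9.7, 12.1 and SAP 7.10. Finally, the opening text of 12.2, the safety management plan and the eCRFs were not available for this check. They may say how mild findings are recorded, but SAP 7.10 would still not tabulate them.

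**Conclusion.** The point holds for mild sensor-site reactions. Their reportability depends on resolution by 48 hours, which no scheduled observation establishes, and the AE windows disagree. No planned table shows findings that are not AEs. Followed as written, the plan can leave out of its safety tables the reactions that it calls probable and uses to characterise the added risk.

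How many would be lost is unknown: about 1 to 22 among 108 children at assumed rates of 1% to 20%, if every mild reaction were treated as exempt. The reported count could lie anywhere between none and all of them, depending on how sites read the rule. The 108 is a minimum, since training and replaced children also wear the sensor. The consequence is an uninterpretable count of minor device effects. The primary comparison is unaffected, and no bias between arms has been shown.

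**What to change.** - Reconcile Protocol 6.1, 10.9.7, 10.11, 12.1, Table 7 in 12.2.2, 12.3.3, 12.3.4 and SAP 7.10 to one AE window and one statement of how mild skin findings are handled, including whether they fall under Table 7.
- Record the skin check already required at sensor removal for every child by grade, for example none, mild, pronounced, or needing treatment. Recording should not depend on resolution at 48 hours.
- Add to SAP 7.10 a table of these findings by grade and arm, with training children listed separately, whether or not the finding is a reportable AE.

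The cost is protocol and SAP wording, one eCRF item and one table. The examination itself is already required. The small downside is a higher displayed count of minor device effects.

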12.4 Product Complaint Reporting

The reporting of product complaints (device deficiencies-DD) is part of the BTIGER Study and should be done in addition to the AE/DD reporting requirements. It is the responsibility of the investigator to report all product complaints associated with a medical device distributed by Medtronic, regardless of whether they are related to intended use, misuse or abuse of the product. Reporting must be done immediately and via the regular channels for market-released products (Medical Device Reporting [21 CFR 803] in the US).

Product Complaint: Any written, electronic or oral communication that alleges deficiencies related to the identity, quality, durability, reliability, safety, effectiveness or performance of a medical device that has been placed on the market.

Reporting must be done immediately and via the regular channels for market-released products. The reporting of product complaints by the clinical team must be done according to the local Standard Operating Procedures. Medtronic will notify the regulatory authorities as applicable for the following incidents immediately upon learning of them and is not limited to AEs and DDs only:

- Any malfunction or deterioration in the characteristics and/or performance of a device, as well as any inadequacy in the labeling or instructions for use which led or might have led to the death or serious deterioration in the state of health of a patient, user, or other person.

Medtronic Business Restricted

- Any technical or medical reason resulting in withdrawal of a device from the market by the manufacturer.
- Any serious deterioration in the state of health, including:
 - Life-threatening illness or injury
 - Permanent impairment of a body function or permanent damage to a body structure
 - A condition necessitating medical or surgical intervention to prevent permanent impairment of a body function or permanent damage to a body structure

12.5 Device Deficiency

The DD definition is provided in Table 5. DD information will be collected throughout the study and reported to Medtronic. Note that DD that result in an AE to the subject should be captured as an AE only.

13. Data Review Committees

13.1 Clinical Events Committee Review

This study will have the Steering Committee. The Steering Committee is composed of physicians with expertise in the area of Anesthesiology monitoring in pediatric patients, who will assume a leadership role in the overall study. The Steering Committee's roles are to:

- Develop the protocol along with Medtronic, to ensure its scientific and statistical soundness;
- Review the conduct of the study;
- Help identify and resolve problems with recruitment or performance

This study is considered a non-significant risk for study participants. Thus, the need for additional safety oversight beyond Medtronic's already rigorous safety monitoring processes is not required. A Medtronic Medical Advisor, as needed, will provide an independent medical review according to the study Safety and Complaint Management Plan. The Medical Advisor will not be affiliated with an investigative center.

14. Statistical Design and Methods

Statistical analyses will be conducted by Medtronic or its designee as outlined in the Statistical Analysis Plan (SAP.) Any changes in statistical methods will be detailed in the Clinical Study Report. Data exclusion will be captured in the Data Management Plan.

14.1 General Aspects of Analysis

Standard demographic information and baseline characteristics will be summarized using descriptive statistics. For safety assessments, adverse events (AEs) will be summarized using frequency counts and percentages. Descriptive statistics will be provided by severity and relationship as needed.

The primary endpoint will be collected as a continuous variable every minute along with the BIS values. The primary analysis will be based on all evaluable data (excluding training subjects). Normality of data will be tested using the Kolmogorov-Smirnov test. Depending on whether normality assumption holds, a two-group t-test or Wilcoxon rank-sum test will be used to compare between the two treatment groups. A *P*-value of less than 0.05 is considered statistically significant unless otherwise specified.

The training subjects will not be included in the analysis set for the primary and secondary endpoints. The training subjects will be summarized descriptively and separately. Any specific findings from these subjects will be noted and discussed in the study report.

The following secondary endpoints will be evaluated:

- Time to first response (emergence)
- Time to PACU discharge readiness using Modified Aldrete Score
- Time to extubation

Upon meeting the primary endpoint, the secondary endpoints will be evaluated using the Holm-Bonferroni method. The method is a sequentially rejective multiple test procedure used to adjust multiplicity and to ensure the overall type I error rate is controlled at the 0.05 level. For statistical inferences, categorical variables will be evaluated using the Chi-square test or Fisher's exact test, and continuous variables will be evaluated using the t-test or Wilcoxon rank-sum test as appropriate. The analysis details will be clearly specified in the Statistical Analysis Plan.

Data Poolability

The clinical study will be conducted under a common protocol for each investigational site with the intention of pooling the data for analysis. Every effort will be made to promote consistency in study execution at each study site.

An assessment of data poolability of the sites will be performed using a mixed-effect model for the primary endpoint. A significance level of 0.15 will be considered. Sites with fewer than five subjects will be combined into large sites to ensure statistical robustness.

If the sites are found to be significantly heterogeneous with respect to the primary endpoint, additional analyses will be conducted to further assess differences between sites in baseline and procedural variables that might contribute the differences.

Medtronic Business Restricted

Missing Data

The primary analysis will include all evaluable data and missing values will not be imputed. BIS™ values that are outside of the specified range of 45 – 60 during maintenance of anesthesia for >35% of the maintenance duration will be considered a protocol deviation and will result in an exclusion of the subject from the primary analysis. The excluded subject will be replaced, and data from all excluded subjects will be noted and discussed in the final study report. Additionally, sensitivity analysis (e.g., multiple imputation) may be performed as appropriate to assess the robustness of study results.

Additional Summaries and Considerations

Cardiovascular variables will be summarized for both treatment groups. The incidence of hypotension will be summarized and compared to anesthesia sedation levels.

The anesthetic requirements with the BIS™ value, the percentage of time during maintenance with BIS™ value within the specified ranges, and number of episodes and duration of burst suppression will be assessed for the BIS and SP groups.

Additional endpoints, including the PAED scale, PACU discharge readiness and a subgroup analysis for subjects requiring neuromuscular blockade, will be evaluated by using descriptive statistics and compared between both groups.

